3.0 OBJECTIVES, ENDPOINTS, AND ESTIMANDS

Table 2 presents the primary, secondary, and exploratory objectives and corresponding Estimands or endpoints.

Table 2 Study Objectives and Estimands/Endpoints

Objectives	Estimand Description/Endpoints
Primary	
• To investigate the safety and tolerability of the protocol to increase the rate of Fabrazyme infusion with reduced total time and volume of infusion	Population : Participants with confirmed diagnosis of FD, age 2 to 65 years, Fabrazyme-experienced, treated for at least 3 months without IARs during the most recent 3 infusions.
	Treatment : Fabrazyme 1 mg/kg Q2W up to the rate tolerated (refer to Section 6.2), with oral premedications given 30 minutes prior to each infusion.
	Endpoint : % reduction of infusion duration from prestudy average of recent 3 infusions.
	Intercurrent events: A while-on-treatment approach will be applied, where the % reduction of infusion duration will be derived from the infusions actually received. Participants never observed to tolerate any infusion rate will be counted as having zero percent reduction. A treatment policy approach will be applied in case pre-medications are not given as described within the protocol. No action will be taken for this event for the analysis even when pre-medications are not given as described within the protocol.
	Summary measure : Median and quantiles of % reduction of infusion duration from prestudy average of recent 3 infusions.

Objectives	Estimand Description/Endpoints
	Population : Participants with confirmed diagnosis of FD, age 2 to 65 years, Fabrazyme-experienced, treated for at least 3 months without IARs during the most recent 3 infusions.
	Treatment : Fabrazyme 1 mg/kg Q2W up to the rate tolerated (refer to Section 6.2), with oral premedications given 30 minutes prior to each infusion.
	Endpoint : Shortest infusion duration each participant tolerates.
	Intercurrent events: A while-on-treatment approach will be applied, the shortest infusion duration will be derived from the infusions actually received. Participants never observed to tolerate any infusion rate will be counted as having duration greater than the maximum observed in their treatment group. A treatment policy approach will be applied in case pre-medications are not given as described within the protocol. No action will be taken for this event for the analysis even when pre-medications are not given as described within the protocol.

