9.3.2 Primary Endpoint Analysis

Table 5 Primary Endpoint Analysis

Endpoint	Statistical Analysis Methods
% Reduction of infusion duration from prestudy average of recent 3 infusions in participants with confirmed diagnosis of FD, age 2 to 65 years, Fabrazyme-experienced, treated for at least 3 months without IARs during recent 3 infusions.	The primary endpoint will be analyzed using descriptive statistic, focusing on median and quantiles of % reduction of infusion duration from prestudy average of recent 3 infusions (pooled all cohorts).
Shortest infusion duration tolerated by each participant in participants with confirmed diagnosis of FD, age 2 to 65 years, Fabrazyme-experienced, treated for at least 3 months without IARs during recent 3 infusions.	The primary endpoint will be analyzed using descriptive statistic, focusing on median and quantiles of the shortest infusion duration tolerated by each participant (pooled all cohorts).

Abbreviations: FD = Fabry disease; IAR = infusion associated reaction.

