will be applied, the shortest infusion duration will be derived from the infusions actually received. Participants never observed to tolerate any infusion rate will be counted as having duration greater than the maximum observed in their treatment group. A treatment policy approach will be applied in case pre-medications are not given as described within the protocol. No action will be taken for this event for the analysis even when pre-medications are not given as described within the protocol.
Summary measure: Median and quantiles of the shortest infusion duration each participant tolerates.

Document: \\ieedc-

Author:

 $vnasc 01 \\BIOS data \\Sanofi \\Fabrazyme \\IAB16602 \\Biostatistics \\Documentation \\SAP \\Sanofi \\Finally \\Sanofi \\Finally \\Finally$

Version\lps17726-16-1-9-sap.docx

Template No.: CS_TP_BS016 Revision 7

Version Number: Final V1.0

Version Date: 22Oct2024

Reference: CS_WI_BS005

Effective Date: 01Nov2021

Sanofi-Aventis Recherche & Développement PROTOCOL LPS17726

Analysis Plan Template

Page 12 of 65

Secondary		
To investigate the proportion of participants achieving the shortest planned duration of infusion time (20 minutes for participants ≥30 kg and 30 minutes for participants <30 kg) without experiencing any or the second IAR	Population: Participants with confirmed diagnosis of FD, age 2 to 65 years, Fabrazyme-experienced, treated for at least 3 months without IARs during the most recent 3 infusions. Treatment: Fabrazyme 1 mg/kg Q2W up to the rate tolerated (refer to Protocol Section 6.2), with oral premedications given 30 minutes prior to each infusion. Endpoint: Binary: Participant achieved the shortest planned duration of infusion time (20 minutes for participants ≥30 kg and 30 minutes for participants <30 kg) without experiencing any IAR. Intercurrent events: A while-on-treatment approach will be applied. Participants never observed to tolerate any infusion rate will be counted as not achieving the shortest planned duration. A treatment policy approach will be applied in case pre-medications are not given as described within the protocol. No action will be taken for this event for the analysis even when pre-medications are not given as described within the protocol. Summary measure: Number and % of participants achieving the endpoint. Population: Participants with confirmed diagnosis of FD, age 2 to 65 years, Fabrazyme-experienced, treated for at least 3 months without IARs during the	

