3.3 CHANGES TO ANALYSIS FROM PROTOCOL

The following presents the updated changes to analysis from protocol section 9.0, version 2.0 (Protocol Amendment Number 1.0), dated 20May2024.

Table B - Changes to Analysis from Protocol

Analysis in SAP	
Reason for Update: ADA analysis will include summaries of ADA attributes, titer, incidence, and kinetics of ADA response. Also, "6 months follow-up" will include "each visit where plasma lyso-GL3 (ng/mL)/ADA titer is recorded" to make it clear that all post-baseline visits will be considered for analysis as per the windowing convention described in Section 6.6 'Windowing Conventions'. Refer to Section 15.3.1 for the full descriptions of derivations and analyses.	
Reason for Update: Analyses with limited value are removed: The 95% confidence intervals will not be presented due to the small sample size. Shift tables will not be presented. Change from baseline will only be derived for continuous measurements of select variables specified in the SAP. See Section 7: 'Statistical Considerations'	

Document: \\ieedc-

vnasc01\BIOSdata\Sanofi\Fabrazyme\IAB16602\Biostatistics\Documentation\SAP\SAP\Sanofi\Final

[figure not shown]
Version\lps17726-16-1-9-sap.docx

Author: Version Number: Final V1.0

Version Date: 22Oct2024

Template No.: CS_TP_BS016 Revision 7 Reference: CS_WI_BS005

Effective Date: 01Nov2021

Page 23 of 65

Analysis in Protocol	Analysis in SAP
Categorical data will be summarized using count and percentage (the percentage of participants in each category relative to the total number of participants in the relevant analysis set or relative to the total number of participants in the relevant analysis set, with assessments available [where appropriate]) in each category. A 95% CI will be provided for the binary endpoint as appropriate. The change from baseline in distribution for the categorical endpoint_will be presented with a shift table; number and percentage of participants will be provided.	
Analysis of Cohorts ■ The data will be summarized per cohort and by pooled cohorts as described in Sections 9.3.2, 9.3.3 and 9.3.4, and where appropriate, per infusion duration.	Reason for Update: Data will be summarized by pooled cohorts 1-4 only. This is because there are very few participants within each cohort. See Section 7: 'Statistical Considerations'

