7 STATISTICAL CONSIDERATIONS

In general unless otherwise specified, descriptive statistics will be provided on observed cases only eg, for by-visit summaries only participants with non-missing values at that visit will be included in the analysis at that visit. Data will be summarized by cohorts 1-4 pooled. There will be no comparisons between any of the cohorts for all analysis.

The following descriptive statistics will be used as applicable to summarize the study data unless stated otherwise:

Document: \\ieedo

Author:

vnasc01\BIOSdata\Sanofi\Fabrazyme\IAB16602\Biostatistics\Documentation\SAP\SAP\Sanofi\Final

Version Number:

Version\lps17726-16-1-9-sap.docx

Version Date:

Template No.: CS_TP_BS016 Revision 7 Reference: CS_WI_BS005

Effective Date: 01Nov2021

PROTOCOL LPS17726

Analysis Plan Template

Page 31 of 65

- Continuous data will be summarized using the number of observations available (number, arithmetic mean, standard deviation [SD], minimum, median, 1st quartile, 3rd quartile, and maximum).
- Categorical data will be summarized using count and percentage (the percentage of participants in each category relative to the total number of participants in the relevant analysis set or relative to the total number of participants in the relevant analysis set, with assessments available [where appropriate]) in each category.

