7.3.1.1.2 ACTUAL SHORTEST TOLERATED INFUSION DURATION

Participants never observed to tolerate any infusion during the study treatment period will have

Document: \\ieedc-

vnasc01\BIOSdata\Sanofi\Fabrazyme\IAB16602\Biostatistics\Documentation\SAP\SAP\Sanofi\Final

Version\lps17726-16-1-9-sap.docx

Author: Version Number: Final V1.0

Version Date: 22Oct2024

Template No.: CS_TP_BS016 Revision 7 Reference: CS_WI_BS005

Effective Date: 01Nov2021

PROTOCOL LPS17726

Analysis Plan Template

Page 33 of 65

their actual shortest tolerated duration set to their mean (average) pre-study infusion duration. If all pre-study durations are missing and the participant does not tolerate any infusion during the study treatment period, then shortest tolerated infusion duration will be considered missing.

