15.1.3 INTERCURRENT EVENT HANDLING AND DATA IMPUTATION FOR PRIMARY ENDPOINT VARIABLE(S)

Refer to Sections 7.2 and 7.3.1.1 for details about intercurrent events and management of missing data.

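### For a primary endpoint, SAP 7.3.1.1.2 gives non-tolerators their pre-study mean duration (or missing), while the estimand ranks them above the longest duration observed

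*SAP*

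**What the plan says.** **Estimand.** For shortest infusion duration tolerated, Protocol 3.0 (Table 2) says that participants who never tolerate any rate "will be counted as having duration greater than the maximum observed in their treatment group". The Protocol synopsis has the same rule, and SAP Section 2 (Table A) repeats it: "Participants never observed to tolerate any infusion rate will be counted as having duration greater than the maximum observed in their treatment group". The summary measure is the median and quantiles.

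**Derivation.** SAP 7.3.1.1.2 says that such participants have "their actual shortest tolerated duration set to their mean (average) pre-study infusion duration". If all their pre-study durations are missing, the endpoint is missing. SAP 15.1.3 sends the primary analysis to these rules: "Refer to Sections 7.2 and 7.3.1.1 for details about intercurrent events and management of" missing data.

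**Companion primary endpoint.** On percent reduction, Protocol Table 2 states: "Participants never observed to tolerate any infusion rate will be counted as having zero percent reduction". SAP 7.3.1.1.3 makes percent reduction missing when all pre-study durations are missing, with no exception for non-tolerators.

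**Summaries.** SAP Section 7 pools cohorts 1-4 and says that, unless otherwise specified, "descriptive statistics will be provided on observed cases only". Its statistics include mean, SD and maximum as well as the quartiles.

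**Declared changes.** SAP Section 1 points to Section 3.3 for changes to the protocol's statistical considerations. Section 3.3 opens: "The following presents the updated changes to analysis from protocol section 9.0". Its readable entries cover ADA and visit wording, removal of confidence intervals and shift tables, and pooling of cohorts.

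**The concern.** One SAP holds two incompatible rules for the same participants on a primary endpoint, and a programmer cannot follow both. The rule that would be programmed is not the estimand's rule.

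Failure to tolerate is the outcome that this study is designed to detect. Under the SAP rule such a failure enters the summary and the waterfall plot (SAP 15.1.4) as a tolerated duration that the participant did not tolerate in the study. That value need not be the worst in the pooled data, so a failure can be placed ahead of a success. If pre-study durations are all missing, the failure leaves both primary summaries.

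**Working it through.** The documents give no figure for this endpoint, so there is none to reproduce.

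**Inputs.** n = 14 (Protocol 4.1, the maximum). Quartiles follow SAS definition 5; this is an assumption, because the SAP names SAS 9.4 but no percentile definition. Pre-study means of 90 and 120 min are also assumptions: the amendment rationale for Protocol 4.5 (in 10.6) names them as the shortest initial durations for <30 kg and ≥30 kg. All other durations below are invented for illustration.

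**Which rule operates.** SAP 15.1.3 cites 7.2 and 7.3.1.1. Section 7.2 sets a while-on-treatment approach but has no rule for non-tolerators, so 7.3.1.1.2 applies.

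**Link to percent reduction.** SAP 15.1.2 computes 100 × (pre − shortest)/pre. With shortest set to pre, this is 100 × (pre − pre)/pre = 0, as the companion estimand requires. With no pre-study data it is missing, while the estimand still says 0%.

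**Ordering.** A non-tolerator with a 90-min pre-study mean ranks ahead of a participant who tolerated only 120 min. A non-tolerator at 120 min ties with that participant. The same non-tolerator ranks ahead of one whose 120-min infusion took up to 1.2 × 120 = 144 min and still counts as tolerated (SAP 15.1.1.1).

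**Bound when non-tolerators have pre-study data.** For n = 14, Q3 is the 11th value (14 × 0.75 = 10.5) and the median is the mean of the 7th and 8th. Let k be the number of non-tolerators, m their smallest pre-study mean, and s = k plus the tolerators slower than m.

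- Q3, k ≤ 3: the estimand takes the 11th smallest tolerator. The SAP rule gives the same value unless that tolerator exceeds m, which needs at least (14 − k) − 10 = 4 − k tolerators above m. So a difference needs s ≥ 4.
- Median, k ≤ 6: by the same argument on the 8th value, at least (14 − k) − 7 = 7 − k tolerators must exceed m. So a difference needs s ≥ 7.
- From k = 4, Q3 under the estimand lies above the maximum and has no number; from k = 7 the same is true of the median.

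The bound is necessary, not sufficient, because ties can leave the values equal. In 300,000 random datasets with non-missing pre-study means there was no exception.

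**Examples (minutes; NT = non-tolerator).**

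| Assumed data | Statistic | SAP 7.3.1.1.2 | Estimand |
|---|---|---|---|
| 13 at 20; one NT at 120 | median; Q3 | 20; 20 | 20; 20 |
| same | maximum | 120 | above maximum |
| same | mean; SD | 380/14 = 27.1; 26.7 | no number (tolerators only: 20.0; 0) |
| 10 at 20, 3 at 30; one NT at 120 | median; Q3 | 20; 30 | 20; 30 |
| 10 at 20, 2 at 30; two NT at 120 | median; Q3 | 20; 30 | 20; 30 |
| 10 at 20, 3 at 120; one NT at 90 (s = 1 + 3 = 4) | median; Q3 | 20; 90 | 20; 120 |
| 20, 20, 20, 20, 30, 60, 120, 150, 180, 180; four NT at 90, 90, 120, 120 (s = 4 + 4 = 8) | median; Q3 | 90; 120 | 135; above maximum |

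**Missing branch.** Here there is no m and the SAP's n falls to 13, so the bound does not apply. Q3 becomes the 10th value (13 × 0.75 = 9.75) and the median the 7th.

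| Assumed data | Statistic | SAP (n = 13) | Estimand (n = 14) |
|---|---|---|---|
| 10 at 20, 3 at 30; one NT, no pre-study data | Q3 | 20 | 30 |
| 7 at 20, 6 at 30; one NT, no pre-study data | median | 20 | (20 + 30)/2 = 25 |

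**The case against.** The pre-study-mean rule is defensible. The assigned value comes from infusions that eligibility requires to have been free of IARs. It makes the two primary endpoints agree for non-tolerators. It also supplies a number for the mean and SD that SAP Section 7 asks for, which the estimand's rule does not. The estimand has a gap of its own: treatment group is not defined in a single-arm study with four cohorts. Non-tolerators should be few, since the amendment rationale reports good tolerance in the initial 4 participants and a participant must fail every study infusion to qualify. There are no tests, responder flags do not depend on this rule (SAP 7.3.1.2), and listings show each participant's value by cohort.

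Most of this stands. It makes the choice of rule partly a matter of preference and keeps the weight low. It does not remove the contradiction between SAP Table A and SAP 7.3.1.1.2, or the loss of failures without pre-study data.

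A reader might infer more than the documents support:

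- *That the SAP rule shifts the primary result in the product's favour.* The median usually does not move, and the SAP mean (27.1 in the first example) is less favourable than a tolerators-only mean (20.0).
- *That percent reduction is mis-scored for all non-tolerators.* It comes out at 0% whenever any pre-study duration is known.
- *That Section 3.3 was meant to list this change and conceals it.* Its stated scope is Protocol section 9.0, the estimand is in section 3.0, and part of its table is not readable.
- *That the bound is a general reassurance.* It fails in the missing branch.

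**Conclusion.** The point holds as an inconsistency between a primary estimand and its operative derivation, not declared in the readable part of SAP 3.3. It should be fixed, at the low end of that grade.

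In the documents themselves the conflict is certain; its numerical effect depends on data not yet seen. Maximum, mean and SD are exposed from the first non-tolerator, but only the median and quantiles belong to the estimand. Those are unlikely to change if non-tolerators are one or two with pre-study means well above the tolerated durations. Q3 is more exposed than the median. The case with no pre-study data is remote, but it is the one in which a single failure can move either statistic and also disappear from percent reduction. The sizes rest on n = 14, SAS definition 5 and the assumed durations.

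**What to change.** Choose one of two routes.

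**A. Follow the estimand.**
- SAP 7.3.1.1.2: for the median and quartiles, rank non-tolerators above the largest tolerated duration in cohorts 1-4 pooled, also when pre-study data are missing. Print *above maximum* where a quartile or the maximum falls among them, show their number, and label any mean or SD *tolerators only*.
- SAP 15.1.2 and 7.3.1.1.3: state in both that every non-tolerator, with or without pre-study data, has 0% reduction (0% change in the waterfall plot). Otherwise the formula in 15.1.2 loses its input once the duration is only a rank.
- SAP 15.1.4: mark non-tolerators in the duration waterfall plot.
- Table A: state that treatment group means cohorts 1-4 pooled, as SAP 19.1.4 suggests.

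**B. Keep the pre-study mean.** Align SAP Table A with it and declare the departure from the protocol estimand, with the reason, in SAP 3.3. Mark these values in the summary and waterfall plot as not tolerated in the study. Count non-tolerators without pre-study data as 0% reduction, and show their number beside the duration summary.

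**Cost.** Either route needs SAP wording and output labels only, with no new data. Under A a quartile may have no number, and the tolerators-only mean looks more favourable, which is why the label and count are needed. Under B a failure can still rank ahead of a success.

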7.3.1.1.3 Percentage Reduction in Infusion Duration

Percentage reduction of infusion duration, see Section 15.1.2 should be considered missing if all pre-study infusion durations are missing. If at least one is missing (but not all), then available infusion durations will be used.

7.3.1.2 SECONDARY ENDPOINTS

For all secondary endpoints, see Section 15.2.1, participants never observed to tolerate any infusion rate during the study treatment period will be classified as non-responders ie, "No".

7.3.1.3 EXPLORATORY ENDPOINTS

7.3.1.3.1 HANDLING OF ADA TITERS WITH MISSING OR NON-NUMERICAL VALUES

If the ADA titer is reported as "<value", then the actual value is imputed as this value. For example, "<100" will be imputed as 100. However, no imputation for missing or non-numerical values will be done.

7.3.1.3.2 HANDLING OF PLASMA LYSO-GL3 (NG/ML) WITH NON-NUMERICAL VALUES

Results below the quantification limit (QL) of 0.3 ng/ml will be imputed to 0.15 (QL/2) for the summary tables and figures. Listings will present the reported value, as "<0.3 (ng/ml)".

7.3.2 SAFETY ENDPOINTS

No imputation of results will be applied to all safety endpoints.

Document: \\ieedc-

 $vnasc01\BIOS data\Sanofi\Fabrazyme\IAB16602\Biostatistics\Documentation\SAP\SAP\Sanofi\Final$

Version\lps17726-16-1-9-sap.docx

Author: Version Number: Final V1.0

Version Date: 22Oct2024

Template No.: CS_TP_BS016 Revision 7 Reference: CS_WI_BS005

Effective Date: 01Nov2021

Page 34 of 65

7.3.2.1 PARTIAL DATES FOR ADVERSE EVENTS AND MEDICATIONS

Partial missing date and/or time will be imputed to determine start/stop date and time for adverse events and medications. Only the collected date, not the imputed will be present in listings. The imputation conventions are specified in Section 20 Appendix 2 - 'Partial Date Conversions'.

7.3.2.2 ADVERSE EVENTS

7.3.2.2.1 Intensity

If the intensity is missing for one of the occurrences of an AE, for incidence summaries the intensity will be imputed with the maximal intensity of the other occurrences of the same AE for that participant. If the intensity is missing for all occurrences or if there are no other occurrences, the intensity will be left as missing. Actual values as collected will be presented in overview listings of pre-treatment AEs, All TEAEs and post-treatment AEs.

7.3.2.2.2 RELATIONSHIP

If the relationship to study treatment is missing for a pre-treatment or post-treatment AE, then for incidence summaries a relationship of "not related" will be assigned. If the relationship to study treatment is missing for a TEAE, a relationship of "related" will be assigned. Actual values as collected will be presented in overview listings of pre-treatment AEs, All TEAEs and post-treatment AEs.

7.4 MULTIPLE COMPARISONS/ MULTIPLICITY

Multiplicity adjustment is not applicable as no statistical testing is planned.

7.5 EXAMINATION OF SUBGROUPS

No subgroup analyses will be performed for this study.

Document: \\ieedc-

 $vnasc01\BIOS data\Sanofi\Fabrazyme\IAB16602\Biostatistics\Documentation\SAP\SAP\Sanofi\Final$

Version\lps17726-16-1-9-sap.docx

Author: Version Number: Final V1.0

Version Date: 22Oct2024

Template No.: CS_TP_BS016 Revision 7 Reference: CS_WI_BS005

Effective Date: 01Nov2021

PROTOCOL LPS17726

Analysis Plan Template

Page 35 of 65

8 OUTPUT PRESENTATIONS

Section 19 Appendix 1 - 'Programming Conventions' for Outputs shows conventions for presentation of data in outputs.

The templates provided with this SAP describe the presentations for this study and therefore the format and content of the summary tables, listings, and figures to be provided by IQVIATM Biostatistics.

Unless otherwise specified, for eCRF data, unknown as presented on summary outputs corresponds to a missing entry on the eCRF.

